# 9.4 Primary Endpoint s

# 9.4.1 Dose-Finding

The primary objective is to assess the RP2D and the rate of DLTs will be used to determine RP2D. All subjects who receive any study treatment will be included in the final summaries and listings of safety data.

# 9.4.2 Overall Response Rate

Overall response rate (ORR) will be calculated as the sum of subjects achieving any complete response (including CR and CRi) or any partial response (including PR and nPR) divided by the total number of response evaluable subjects. Subjects without a baseline/screening tumor assessment or at least one on-treatment assessment will be considered non-responders. Each value will be reported along with a one-sided 95% exact binomial confidence interval. No hypothesis testing will be performed for ORR.

# 9.4.2.1 Rationale to Use ORR as Endpoint

The decision to use ORR as the endpoint is based on multiple phase III clinical trials that have not shown a correlation between PFS and OS outcomes to CR rates. In Burger et al, elderly treatment-naïve CLL patients were randomized to receive either ibrutinib or chlorambucil. CR rates for ibrutinib were 4% and 2% for chlorambucil yet ibrutinib had improved 18-month PFS and 24-month OS by 38% (hazard ratio [HR] 0.16; 95% confidence interval [CI] 0.09 – 0.28; p<0.001) and 14% (HR 0.16; 95% CI 0.05 – 0.56; p=0.001), respectively. Similarly in R/R CLL patients, a phase III trial comparing ibrutinib vs. ofatumumab showed low CR rates of 2% and 1%, respectively. In an updated analysis, ibrutinib-treated patients had a median PFS of 44.1 months as compared to 8.1 months for ofatumumab-treated patients (HR 0.148; 95% CI 0.113 – 0.196; p<0.001). Rituximab/venetoclax vs. rituximab/bendamustine was studied in the MURANO trial for R/R CLL patients. Independent-review committee CR rates for rituximab/venetoclax was

8.2% as compared to 3.6% for patients treated with rituximab/bendamustine. An updated 36 month median follow up showed an improvement in 36 month PFS of 56.2% (HR 0.16; 95% CI 0.12 – 0.23; p<0.001) for patients treated with rituximab/venetoclax as compared to patients treated with rituximab/bendamustine as well as 36 month OS of 87.9% vs. 79.5% (HR 0.50; 95% CI 0.30 – 0.85; p=0.0093). Lastly, precedence to use ORR as the primary endpoint for a R/R CLL phase II trial exists with venetoclax.

## 9.5 Secondary Endpoints

#### 9.5.1 Safety and Tolerability

All subjects who receive any study treatment will be included in the final summaries and listings of safety data. The detailed information collected for each AE will include a description of the event, duration, severity, relatedness to study drugs, action taken, and clinical outcome. The severity of the AEs will be graded according to the CTCAE v5.0. The statistical analysis of the safety data will be descriptive and tabular.

#### 9.5.2 Duration of Response

The duration of response (DoR) will be defined as the time from the first documented response (CR, CRi, PR or nPR per iwCLL) until the time of progression, the start of a new therapy, or death from any cause. Kaplan-Meier methods will be used to analyze DoR and will be presented with 95% confidence intervals. Table 22 defines the date of progression or censoring that will be utilized for the analysis. No formal hypothesis testing will be performed.

Situation	Date of Progression or Censoring	Outcome
Incomplete or no baseline tumor assessments	Date of registration	Censored
Progression documented between scheduled visits	
 
Earliest of:
 
Date of progression assessment showing new lesion (if progression is based on new lesion); or
 
Date of last progression assessment.
 
	Progressed
No progression	Date of last progression assessment with no documented progression	Censored
Treatment discontinuation for undocumented progression	Date of last progression assessment with no documented progression	Progressed
New anticancer treatment started	Date of last progression assessment with documented non-progression before the start of new treatment	Progressed

 Table 22: Duration of Response
 Censoring Criteria

Death before first PD assessment	Date of death	Progressed
Death between adequate assessment visits	Date of death	Progressed
Death or progression after more than one missed visit	Date of last progression assessment with documented non-progression	Progressed

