 At C5D1 (±7 days): CT scans of the neck, chest, abdomen and pelvis should be performed with contrast agents unless contraindicated for medical reasons. Should this CT show that the patient has achieved an iwCLL 2018 defined complete remission and absolute lymphocyte count is <4000, then a bone marrow biopsy should be performed at this time to confirm the complete remission. At any other study time point beyond C5D1 (excluding end of treatment): If patient achieves hematologic recovery or the treating physician suspects the patient has achieved a complete remission per the 2018 iwCLL criteria, then a peripheral blood immunophenotype should be ordered. Should this show no evidence of circulating CLL cells, then a complete remission can be confirmed with CTs of the neck, chest, abdomen and pelvis along with a bone marrow biopsy. If CTs and bone marrow biopsy are indicated, studies need to be performed within 28 days.

 If subject achieves hematologic recovery or the treating physician suspects the patient has achieved a complete remission as per the 2018 iwCLL criteria, then a peripheral blood immunophenotype should be ordered. Please refer to reference **20** for sequencing of testing to confirm a complete remission.

 The bone marrow biopsy performed at screening should be after progression is noted from most recent line of therapy and within 6 months of screening. If a bone marrow biopsy is not performed at screening, an archival tissue maybe requested at the discretion of the PI. BM CLL MRD by NGS should be performed on any BM aspirate obtained after screening.

 Should peripheral blood immunophenotying show no evidence of circulating CLL cells, then a complete remission can be confirmed with CTs of the neck, chest, abdomen and pelvis and a bone marrow biopsy. Please refer to reference **20** for sequencing of testing to confirm a complete remission.

 BMBx at screening and EOT are the only ones required on study. If a prior bone marrow biopsy showed the patient to be in a complete remission, a repeat bone marrow biopsy is not required unless progression of disease is suspected.

 Samples should be collected prior to dosing of the drugs. Samples should be collected on C1D1, C1D8, C1D15, C2D1, C2D8 and at time of progression.

 Refer to section **1.5.1** for time points

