2.2.3 To assess overall survival (OS) in this study population

Secondary Endpoint: OS as defined as the time from registration until death from any cause.

2.2.4 To assess the duration of response (DoR) of the study population.

Secondary Endpoint: DoR as defined as the interval of time from the date of initial documented response (PR or better as per 2018 iwCLL criteria for response) to the time of progression from the best response, the start of a new therapy, or death from any cause.

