# 5.3 Registration

Subjects must meet all of the eligibility requirements before registration. Study-related screening procedures can only begin once the subject has signed the consent form. Subjects must not begin protocol treatment prior to registration.

Treatment should start within 14 days after registration.

To register eligible subjects on study, complete a Clinical Trials Office Subject Registration Form and submit to [contact].

For sites outside of Huntsman Cancer Institute, submit registration forms to [contact]

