# 9.5.3 Progression-Free Survival

Progression-free survival (PFS) will be defined as the time from treatment initiation until documented clinical or radiographic progression or death from any cause. Kaplan-Meier methods will be used to analyze PFS and will be presented with 95% confidence intervals. Table 23 defines the date of progression or censoring that will be utilized for the analysis. No formal hypothesis testing will be performed.

Situation	Date of Progression or Censoring	Outcome
Incomplete or no baseline tumor assessments	Date of treatment initiation	Censored
Progression documented between scheduled visits	
 
Earliest of:
 
Date of progression assessment showing new lesion (if progression is based on new lesion); or
 
Date of last progression assessment.
 
	Progressed
No progression	Date of last progression assessment with no documented progression	Censored
Treatment discontinuation for undocumented progression	Date of last progression assessment with no documented progression	Progressed
New anticancer treatment started	Date of last progression assessment with documented non-progression before the start of new treatment	Progressed
Death before first PD assessment	Date of death	Progressed
Death between adequate assessment visits	Date of death	Progressed

Death or progression after more than one missed visit	Date of last progression assessment with documented non-progression	Progressed	
---	---	------------	--

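### Table 22 censors duration of response at registration, before the response that starts the clock, so any responder whose baseline is judged incomplete would contribute nothing to the estimate

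*Combined protocol and SAP*

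**What the plan says.** Section 9.5.2 defines DoR as the "time from the first documented response (CR, CRi, PR or nPR per iwCLL") to progression, new therapy or death. Section 2.2.4 has the same starting point: "DoR as defined as the interval of time from the date of initial documented response". The analysis is Kaplan-Meier with 95% confidence intervals and no formal test.

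The first row of Table 22 in section 9.5.2 covers patients with "Incomplete or no baseline tumor assessments". It gives their date as "Date of registration" and their outcome as censored.

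Table 23 in section 9.5.3 has the same row for PFS, but with "Date of treatment initiation" as the date. That is the PFS time origin.

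Two other provisions bear on the row:

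- Section 5.3: "Subjects must not begin protocol treatment prior to registration". It also asks for treatment to start within 14 days of registration.
- Section 9.4.2: "Subjects without a baseline/screening tumor assessment or at least one on-treatment assessment will be considered non-responders". It is silent on a baseline that exists but is incomplete.

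**The concern.** A censoring date should fall on or after the time origin of the endpoint. In this row it cannot. Registration comes before treatment, and treatment comes before any on-study response, so every responder who reaches the row is assigned a negative duration.

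What is at stake is whether DoR describes the patients who responded. In a single-arm phase II part with ORR as its primary endpoint, DoR shows whether the responses last, and a reader will assume that the two rest on the same responders. If the row is followed literally, a responder can count in the ORR numerator while all later follow-up, including a progression or death, is lost from the DoR curve. Nothing in the reported estimate would reveal this.

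**Working it through.** The plan gives no figure for this point, so there is none to reproduce. The check is date arithmetic, followed by a test of how Kaplan-Meier treats the resulting times.

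**Who can reach the row**

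- *No baseline.* Section 9.4.2 makes these patients non-responders. They have no DoR, so the row is void for them.
- *Incomplete baseline.* Section 9.4.2 does not mention them, and neither table defines the term. Section 7.4.1 lists blood count, CT, immunophenotyping and marrow as the disease assessments. Footnote 22 of the Schedule of Events foresees a missing screening marrow: "If a bone marrow biopsy is not performed at screening, an archival tissue maybe requested at the discretion of the PI". Under section 7.5.2, a partial remission can be reached from nodes, lymphocytes and blood counts. On one reading, then, a patient without a screening marrow has an incomplete baseline and can still be a counted responder.

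**Inputs**

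- Registration to C1D1: 0 to 14 days (section 5.3).
- Cycle length: 21 days (section 6.1).
- First scheduled on-treatment CT: C4D1 ± 7 days in section 7.4.2, but C5D1 ± 7 days in footnote 20 of the Schedule of Events. The two places disagree, so both are computed.

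**Assigned duration**

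DoR = registration date - first response date = -(gap from registration to C1D1 + days from C1D1 to response).

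Days from C1D1 to the CT: (4 - 1) × 21 = 63 for C4D1, and (5 - 1) × 21 = 84 for C5D1.

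| First CT | Shortest | Longest |
|---|---|---|
| C4D1 | -(0 + 63 - 7) = -56 days | -(14 + 63 + 7) = -84 days |
| C5D1 | -(0 + 84 - 7) = -77 days | -(14 + 84 + 7) = -105 days |

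The overall range is -56 to -105 days. The sign does not depend on which CT visit is right: it is negative for any on-treatment response.

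**Effect on the Kaplan-Meier estimate**

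Twelve invented responders were used, with times in months: events at 2, 4, 7, 9, 12, 14 and 18, and censoring at 5, 10, 15, 20 and 22. The first estimates are 11/12 = 0.917, × 10/11 = 0.833, × 8/9 = 0.741, × 7/8 = 0.648 and × 5/6 = 0.540. One, two or three further responders were then added, censored at -2.8 months. Every risk set and every estimate stayed the same. Replacing -2.8 with 0 also changed nothing. A record censored at or before time zero is in no risk set at any event time, so it carries no information whether the software keeps or deletes it.

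**Scale**

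At the 60% target ORR, 24 × 0.60 = 14.4, or about 14 responders. Each responder lost is 1/14, about 7% of the DoR set. The documents give no rate of incomplete baselines. As an assumed range of 0 to 3 affected responders, the loss is 0% to 3/14, about 21%.

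**The case against.** The strongest reply is that the row may never catch anyone. Node, spleen, liver and lymphocyte responses are all judged against baseline. If incomplete means too little baseline to judge response, these patients are non-responders in practice and never enter DoR. The row is then harmless text carried in parallel with the PFS table. The protocol also points to few gaps: section 7.4.2 wants a baseline CT for all patients, footnote 24 of the Schedule of Events lists the screening marrow as required, and section 7.4.5 requires screening immunophenotyping. This reply stands as far as the number affected is concerned. It does not rescue the date, and it depends on a definition that the plan does not give.

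A reader might infer more than the documents support in three places:

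- *That Table 17 accepts a missing baseline marrow for a partial remission.* Its entry allowing the marrow not to be done is in the partial remission column and describes the marrow at response, not at screening.
- *That a missing screening marrow definitely triggers the row.* Footnote 22 accepts a marrow from the previous 6 months and provides for archival tissue. It does not call such a baseline incomplete.
- *That negative times distort the curve in addition to losing patients.* They do not. Omission of the affected responders is the only effect. The plan does not say how negative times would be handled, so even omission is an inference, but it holds whichever way the record is processed.

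**Conclusion.** The row is wrong as written. Its censoring date always precedes the DoR time origin, and the PFS table shows the same row anchored correctly to its own origin, which suggests a drafting slip. For patients with no baseline it has no effect. For a responder judged to have an incomplete baseline it assigns about -56 to -105 days at the first scheduled CT and removes all follow-up, so the DoR set can be smaller than the ORR numerator.

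The date error rests on the text alone. The day range rests on response being documented at the scheduled CT within its window and on treatment starting within 14 days of registration. The claim that anyone is affected rests on a responder's baseline being classed as incomplete. That number is not in the documents and may be zero, so a definite loss of responders should not be read into the plan. DoR is secondary and descriptive. The primary ORR, dose selection and the safety analyses are untouched. This is worth correcting because it is clear and cheap, not because a large effect has been shown.

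**What to change.** Delete the first row of Table 22. Add one sentence to section 9.5.2: every patient counted as a responder under section 9.4.2 is analysed for DoR from first documented response under the remaining rows, even if a baseline component is missing. Patients with no baseline lose nothing, because they are already non-responders. Responders with a partial baseline keep their follow-up and their events.

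Do not move the censoring date to first response instead. That removes the negative sign but gives zero time, which is the same as excluding the patient.

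It would also help to state in section 9.4.2 which missing baseline components prevent a response from being called, since that decides who is a responder in the first place.

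The cost is one table row and one or two sentences in the statistical section. No visit, procedure, treatment or sample size changes.

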# 9.5.3 Progression-Free Survival

Progression-free survival (PFS) will be defined as the time from treatment initiation until documented clinical or radiographic progression or death from any cause. Kaplan-Meier methods will be used to analyze PFS and will be presented with 95% confidence intervals. Table 23 defines the date of progression or censoring that will be utilized for the analysis. No formal hypothesis testing will be performed.

Situation	Date of Progression or Censoring	Outcome
Incomplete or no baseline tumor assessments	Date of treatment initiation	Censored
Progression documented between scheduled visits	
 
Earliest of:
 
Date of progression assessment showing new lesion (if progression is based on new lesion); or
 
Date of last progression assessment.
 
	Progressed
No progression	Date of last progression assessment with no documented progression	Censored
Treatment discontinuation for undocumented progression	Date of last progression assessment with no documented progression	Progressed
New anticancer treatment started	Date of last progression assessment with documented non-progression before the start of new treatment	Progressed
Death before first PD assessment	Date of death	Progressed
Death between adequate assessment visits	Date of death	Progressed

Death or progression after more than one missed visit	Date of last progression assessment with documented non-progression	Progressed	
---	---	------------	--

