2.2.2 To assess progression-free survival (PFS)

Secondary Endpoint: Progression-free survival (PFS) as defined as the time from study drug initiation to the time documented disease progression (as assessed by 2018 iwCLL criteria) or death from any cause.

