# 7.4.2 Disease Assessment Algorithm

All patients should have a CT scan of the neck, chest, abdomen, and pelvis with IV contrast at the time of screening or up to 28 days prior to C1D1. CTs are required at C4D1 (± 7 days). Should this CT show that the patient has achieved an iwCLL 2018 defined complete remission (CR) and absolute lymphocyte count is <4000, then a bone marrow biopsy should be performed to confirm CR.

At any other study time point beyond C4D1 excluding end of treatment, the patient may have a disease assessment if the subject achieves hematologic recovery or the treating physician suspects the patient has achieved a CR as per the 2018 iwCLL criteria. At that time, a peripheral blood immunophenotype should be ordered. If the peripheral blood

immunophenotype shows no evidence of circulating CLL cells, then CTs of the neck, chest, abdomen, and pelvis should be performed. Should the CT also confirm CR, then a bone marrow biopsy should be performed to confirm CR. The study team has 28 days to complete all necessary testing required to confirm a CR from the time a CR is suspected by the treating physician. During this time, protocol treatment may continue as prescribed.

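### PFS Table 23 censors patients with an incomplete or missing baseline at treatment initiation with no exception for death, in conflict with the PFS definition and the table's own death row; no precedence is stated

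*Combined protocol and SAP*

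**What the plan says.** Section 9.5.3 defines PFS as "the time from treatment initiation until documented clinical or radiographic progression or death from any cause". Section 2.2.2 agrees on death: "the time from study drug initiation to the time documented disease progression (as assessed by 2018 iwCLL criteria) or death from any cause". Neither definition makes an exception for patients whose baseline work-up is lacking.

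Section 9.5.3 then hands the event and censoring dates to Table 23 (listed as Table 24 in the List of Tables). Three of its rows matter here:

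- **First row.** Situation: "Incomplete or no baseline tumor assessments". Date: "Date of treatment initiation". Outcome: censored.
- **Early-death row.** Situation: "Death before first PD assessment". Date: the date of death. Outcome: progressed, that is, an event. It sets no condition on baseline.
- **Missed-visit row.** A death or progression after more than one missed visit is an event, dated back to the last assessment that showed no progression.

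The table gives no order of precedence and does not define an incomplete baseline. Section 9.2 puts every patient who has had one dose into all efficacy sets, so a patient with a deficient baseline stays in the PFS analysis.

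**The concern.** A dosed patient with a deficient baseline who dies early fits two rows with opposite outcomes. Two programmers could each follow the plan and report different PFS curves.

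Applying the first row as written discards a death that the endpoint definition counts. The row is also not confined to early deaths: read literally, it sets aside a death at any later time in such a patient. A missing baseline can make some kinds of progression impossible to judge, which is a fair reason to censor a patient for whom nothing else is known. It does not make a death uncertain. With about 24 patients, the handling of one patient visibly moves a landmark estimate.

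**Working it through.** **1. Apply the text to one patient.** Suppose a patient takes at least one dose, has a baseline that counts as incomplete, misses no visits and dies on day 60.

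| Source | Result |
|---|---|
| PFS definition, 9.5.3 and 2.2.2 | Event on day 60 |
| Table 23, first row | Censored on day 0 |
| Table 23, early-death row | Event on day 60 |
| Section 9.2 | Patient stays in the efficacy set |

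If a progression assessment had already taken place, the row for death between adequate assessments would apply instead. It also gives an event on the date of death, so the conflict remains.

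**2. What day-0 censoring does.** A patient censored at time zero leaves the Kaplan-Meier risk set before the first event and contributes neither an event nor person-time. With complete follow-up to a landmark, the estimate is

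S = (number progression-free at the landmark among those kept) / (N − k),

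where k is the number censored at day 0.

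**3. Size.** The plan gives no PFS rate, event count or power, so there is no figure of its own to reproduce. N = 24 is the planned dose expansion (Section 9.1.1). Twelve progression-free at the landmark and k = 1 to 3 are assumptions. If all k patients are early deaths:

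- k = 0: 12/24 = 50.0%
- k = 1: 12/23 = 52.2%
- k = 2: 12/22 = 54.5%
- k = 3: 12/21 = 57.1%

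If the one censored patient was instead progression-free at the landmark: 11/23 = 47.8%.

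**4. Product-limit check.** Twenty-four event times were set at exponential quantiles, with complete follow-up. The assumed median was 6 or 9 months. That is the background range in Section 3.2 for other treatments, not a design assumption of this trial. The k earliest events were treated as deaths in patients with a deficient baseline and censored at day 0.

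| Assumed median | Landmark | k = 0 | k = 1 | k = 2 | k = 3 |
|---|---|---|---|---|---|
| 6 months | 3 months | 70.8% | 73.9% | 77.3% | 81.0% |
| 6 months | 6 months | 50.0% | 52.2% | 54.5% | 57.1% |
| 9 months | 3 months | 79.2% | 82.6% | 86.4% | 90.5% |
| 9 months | 6 months | 62.5% | 65.2% | 68.2% | 71.4% |

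Events fall from 24 to 23, 22 and 21. The shift is about 2 to 4 points per affected early death. If the deaths are counted on their dates, the estimates stay at the k = 0 column whatever k is.

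**The case against.** The strongest reply is that the early-death row is itself unconditional and agrees with the PFS definition. A sensible analyst would let the death rows govern deaths and keep the first row for patients with no death on record. It follows that a reader should not infer that Table 23 certainly removes these deaths. The table does not say that the censoring row prevails. What remains is that it does not say the opposite either, and the first row taken alone gives the wrong result.

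Four further inferences are tempting, and the documents do not support them:

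- **That an incomplete baseline will be common.** Footnote 22 to the Schedule of Events does foresee a missing marrow: "If a bone marrow biopsy is not performed at screening, an archival tissue maybe requested at the discretion of the PI". But footnote 24 lists the screening marrow among the required biopsies, Table 17 allows PR with no marrow done, and screening CT is planned for everyone. Section 7.4.2 times that CT "at the time of screening or up to 28 days prior to C1D1", while the Schedule allows 42 days for screening. This is a difference in windows; it does not make a CT already obtained an incomplete baseline.
- **That a new lesion is an event without any baseline.** Section 7.5.3 depends on a lesion appearing. At a site never assessed at baseline, disease that was already there cannot be told from new disease.
- **That PFS is necessarily biased upward because such patients are the sickest.** Nothing in the documents says so. Eligibility requires ECOG 0-2 and an expected survival of at least 12 months, and the 47.8% case shows that the shift can go down.
- **That ORR treats the same patients in the opposite way.** Section 9.4.2 makes non-responders of patients with no baseline assessment or no on-treatment assessment. It does not mention an incomplete baseline, so the contrast is exact only where baseline is missing altogether.

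The consequences are also limited. PFS is secondary with no formal test, and OS in Section 9.5.4 has no baseline rule, so every death remains visible there. For scale, the plan's own ORR precision table puts the one-sided 95% lower bound for 12/24 at 31%, 19 points below the estimate. A shift of about 2 points is small beside that.

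**Conclusion.** The conflict is in the text and does not depend on the illustration. The first row of Table 23 censors at treatment initiation with no exception for death, the PFS definition and the early-death row make the same death an event, and nothing says which prevails. If the first row is applied, deaths in dosed patients are dropped from PFS.

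One early death so handled moves a 50.0% landmark estimate to 52.2%. This rests on N = 24, complete follow-up to the landmark and one affected patient. The documents do not give the number affected, which is probably small, and the direction depends on whether those patients fail early. The point is worth correcting because the plan contradicts its own endpoint and the repair is nearly free, not because a large bias has been shown.

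**What to change.** Amend Section 9.5.3 and Table 23 before PFS is analysed:

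1. State that death from any cause is a PFS event on the date of death regardless of baseline completeness, subject to the existing missed-visit row.
2. Limit the first row to patients with no adequate baseline and no documented death. Histologically confirmed transformation may likewise be kept as an event. New lesions should not be given the same exemption unless the site was assessed at baseline.
3. Say which missing baseline component makes progression unassessable, so that the first row does not turn on an undefined word.

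The cost is plan wording only, with no added visits, data or patients. The downside is that PFS may be slightly shorter than it would be if the first row were applied to patients who die.

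### Tables 22 and 23 date three kinds of event at an earlier assessment that showed no progression, and Table 23 counts two events that the PFS definition does not

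*Combined protocol and SAP*

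**What the plan says.** Section 9.5.3 runs PFS from treatment initiation "until documented clinical or radiographic progression or death from any cause"; Section 2.2.2 gives the same two kinds of event. Section 9.5.2 runs DoR from first documented response "until the time of progression, the start of a new therapy, or death from any cause", and Sections 2.2.4 and 4.6 also name new therapy as an end of response.

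Table 22 (DoR) and Table 23 (PFS) then fix date and status by situation (the contents list numbers them 23 and 24). Three rows, the same in both tables, carry the status *Progressed*:

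- "Treatment discontinuation for undocumented progression", dated "Date of last progression assessment with no documented progression".
- New anticancer treatment, dated "Date of last progression assessment with documented non-progression before the start of new treatment".
- "Death or progression after more than one missed visit", dated at the last assessment that documented non-progression.

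The other two death rows use the date of death.

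Table 22 also has a row "Incomplete or no baseline tumor assessments", censored at registration. Section 9.4.2 says: "Subjects without a baseline/screening tumor assessment or at least one on-treatment assessment will be considered non-responders".

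On follow-up, Section 4.6 follows PFS to progression or death, while Section 6.9.4 ends disease assessments at progression or subsequent anticancer therapy. OS starts at registration in Sections 1.1 and 2.2.3 but at treatment initiation in Section 9.5.4. OS follow-up is 10 years in Section 6.9.4 and at least seven in Section 9.5.4, which also censors living patients at five years.

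**The concern.** The last progression-free assessment is a natural date for censoring. Paired with an event status, it records a failure on a day when the patient was known not to have failed. The clearest case is a patient who dies after two missed visits: the death date is known, yet the table replaces it with an earlier day on which the patient was alive and progression-free.

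For PFS there is a second problem. Two of the three rows are neither documented progression nor death, so an analyst who follows the definition and one who follows Table 23 would produce different curves from the same data. With no control arm, the curves are read on their own, and a dating rule that works in one direction is not cancelled by a comparison.

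**Working it through.** The plan gives no sample size, power or event figure for PFS, DoR or OS, so there is no figure of its own to reproduce. The check has two parts.

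**1. Rows against definitions**

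| Row (status *Progressed*) | PFS, Table 23 | DoR, Table 22 |
|---|---|---|
| Death or progression after more than one missed visit | valid event, wrong date | valid event, wrong date |
| New anticancer treatment | not an event as defined; also backdated | defined event, but dated before its start |
| Discontinuation for undocumented progression | not an event as defined; also backdated | backdated; status not clearly in conflict, since 9.5.2 does not require documentation |

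The incomplete-baseline row of Table 22 censors at registration, before first response, when the DoR clock starts.

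**2. Size**

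Shift for one patient in the missed-visit row, taking each scheduled visit as a progression assessment (Section 7.5.3 allows progression on examination and blood counts). Two missed visits span two to three intervals:

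- 21-day cycles: 42 to 63 days, /30.44 = 1.4 to 2.1 months.
- Three-monthly follow-up (Section 1.4, year 1): 6 to 9 months.
- Example: last progression-free assessment at month 6, visits at 9 and 12 missed, death at 13. The definition gives 13 months and the table 6, a difference of 7.

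Effect on the curve. Assumptions: exponential PFS; median 6 or 9 months (the range Section 3.2 quotes for chemotherapy or lenalidomide-based treatment); visits every 21 days to day 378 (18 x 21), then every 91.3 days; 10% or 20% of patients in the rows named; 400,000 simulated patients. True 12-month PFS is 2^(-12/6) = 25.0% and 2^(-12/9) = 39.7%. The simulation is accurate to about 0.1 point.

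*Missed-visit row*

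| Median | As defined | 10% in row | 20% in row |
|---|---|---|---|
| 6 months: 12-month PFS | 25.1% | 23.8% | 22.4% |
| 6 months: median | 6.02 | 5.86 | 5.66 |
| 9 months: 12-month PFS | 39.7% | 38.1% | 36.6% |
| 9 months: median | 9.01 | 8.88 | 8.69 |

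The loss is 1.3 to 3.1 points at 12 months and 0.1 to 0.4 months in the median.

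*New-therapy and undocumented-progression rows, with documented progression or death 1 or 3 months after the trigger*

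| Rule | Median 6 | Median 9 |
|---|---|---|
| Table 23 as written | 23.4-24.6% | 37.9-39.3% |
| Event dated at the trigger | 23.5-24.7% | 38.1-39.4% |
| Censored at last progression-free assessment | 27.5-31.9% | 42.7-47.1% |

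Against 25.0% and 39.7%, the table is 0.4 to 1.8 points low and censoring about 2.5 to 7.4 points high. Table against event-at-trigger isolates the dating: 0.1 to 0.2 points.

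*Same rows, trigger unrelated to progression.* If a share f of patients has the trigger first, counting it as an event gives S^(1/(1-f)). For f = 0.1 and 0.2 this is 0.25^1.111 = 21.4% and 0.25^1.25 = 17.7%; 0.397^1.111 = 35.8% and 0.397^1.25 = 31.5%. The fall of 3.6 to 8.2 points comes from status. Backdating adds only 0.1 to 0.3 (simulated: 17.4-21.3% and 31.2-35.7%).

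*Scale.* The 95% half-width is 1.96 x sqrt(S(1-S)/24) = 17.3 points at S = 0.25 and 19.6 at S = 0.40.

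**The case against.** The strongest reply is that the tables are explicit and prespecified, so the analyst has a rule, and it leans against the drug. Counting new therapy as a failure is a legitimate choice, and for DoR it is the defined event. PFS and DoR are descriptive, no sample size or stopping rule uses them, and the shifts are small beside the sampling error. Most of this stands, and it sets the severity. It does not rescue the backdated death or progression, nor a definition and a table that disagree within one section.

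Four stronger readings are tempting and are not supported:

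- **That counting the two PFS rows as events is wrong in itself.** It is a choice to declare. The defect is that text and table declare different things.
- **That the remedy is to censor both rows.** Censoring at the last assessment and ignoring later deaths would itself depart from a definition that counts every death. Where progression or death soon follows, it is further from that definition than the table, and in the optimistic direction.
- **That shifts of years are likely.** Two missed 12-monthly visits would move a date by 24 to 36 months, but only for patients progression-free more than five years after the last dose. At a 9-month median, 2^(-60/9) = 1.0% reach 60 months, or 0.24 of 24.
- **That the OS analysis is biased.** Ten years of follow-up satisfies at least seven, and five-year censoring can be an analysis cut-off. It leaves later deaths unused but does not distort the curve to year five. The two origins are about 14 days apart at most if treatment starts as Section 5.3 plans.

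The registration row should also hold few patients: screening CT is required, and those with no baseline are non-responders.

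**Conclusion.** The point holds as a low-severity correction. Three rows in each table pair an event status with a progression-free date. In Table 23, two of them also conflict in status with the PFS definition.

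Measured against the written definitions, the dating error only shortens PFS and DoR. In the illustration the missed-visit row costs about 1.3 to 3.1 points of 12-month PFS and 0.1 to 0.4 months of the median. For the other two rows the dating is worth about 0.1 to 0.3 points; anything larger depends on whether they count as events and on how closely the trigger is tied to progression. These figures rest on exponential PFS, medians of 6 to 9 months, and 10 to 20% of patients in the rows. The plan gives no such share. The primary endpoint and N=24 are unaffected. The OS wording is a separate and minor matter of consistency.

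**What to change.** **Both tables.** Date deaths and documented progressions when they occur, also after missed visits. Run censoring after more than one missed visit as a sensitivity analysis.

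**Table 22 (DoR).** Date new therapy at its start. If discontinuation for undocumented progression stays an event, date it when it happens. Replace the registration row: patients with no baseline do not enter DoR, and a responder with an incomplete baseline follows the other rows from first response.

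**PFS.** Before the data are analysed, make Section 9.5.3 and Table 23 agree, in one of two ways:

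- add new therapy and discontinuation for undocumented progression to the definition, as events dated when they occur; or
- keep the definition, so that neither is an event and later documented progression or death counts at its own date, where follow-up allows.

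Report censoring at the last progression-free assessment only as a sensitivity analysis, and say that it can overstate PFS. Reconcile Sections 4.6 and 6.9.4 on PFS follow-up after new therapy.

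**OS (minor).** State one origin in Sections 1.1, 2.2.3 and 9.5.4, and say whether five years is the intended analysis cut-off given the longer follow-up.

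**Cost.** Wording in Tables 22 and 23, Sections 9.5.2 to 9.5.4, 4.6 and 6.9.4, and the objectives and synopsis where a definition changes. New therapy and survival status are already to be recorded (Sections 7.1.4 and 6.9.4). Only following disease status beyond new therapy, as Section 4.6 can be read, would add assessments.
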